# 10.2.3 Monitoring for Hypersensitivity

Recomodulin is a protein product and could therefore cause shock, anaphylactoid symptoms, and similar conditions. The investigator or subinvestigator should therefore closely observe the subject during Recomodulin administration. If anaphylaxis is suspected based on skin symptoms such as urticaria, gastrointestinal symptoms, respiratory symptoms such as dyspnea, or disturbance of consciousness and the like, immediately discontinue Recomodulin administration and provide intervention according to "The manual for handling disorders due to adverse drug reactions-focus on the anaphylaxis" (March 2008, Ministry of Health, Labour and Welfare) (Figure 10.2-1).

[figure not shown]

Figure 10.2-1 Procedures for treating anaphylaxis 16)

# 10.3 Actions to Take for Serious Adverse Events

# 10.3.1 Procedures for Investigator or Subinvestigator

When a serious adverse event occurs, the investigator or subinvestigator will promptly notify the sponsor and study site director orally or by telephone, fax, or a similar means regardless of the causal relationship to the investigational product. The sponsor will be notified no later than 24 hours after a serious adverse event is identified.

The investigator will complete a written report about each serious adverse event (using the specified form of the study site or sponsor) for submission to the sponsor and study site director. With the first reporting day as Day 0, the investigator will submit the written report to the sponsor by Day 4 if the event is a death or life threatening or by Day 7 if the event is another serious adverse event.

The investigator or subinvestigator will comply with any instructions of the study site director based on the findings of the institutional review board about whether the study should continue and the instructions of the sponsor about amending the protocol or taking other appropriate actions.

# 10.3.2 Sponsor Procedures

On receiving a written report of a serious adverse event from the investigator, the sponsor will consult with the medical expert as necessary to deliberate whether the study should be continued or suspended and the need to change the protocol or amend the reference informed consent form.

After this deliberation, the sponsor will notify the regulatory authorities, study site directors, and investigators by the specified deadlines as necessary.

# 10.3.3 Emergency Protocol Deviations/Modifications and Emergency Key Unblinding

The investigator or subinvestigator may deviate from or modify the protocol without the prior agreement of the sponsor and prior approval of the institutional review board in a medically unavoidable situation such as to avoid exposing a subject to acute risk (Section 13.2). The investigator or subinvestigator may request unblinding of the emergency key when finding this to be necessary to ensure subject safety (Section 6.7).

# 10.4 Actions to Take for Identified Pregnancies

The investigator or subinvestigator will discontinue any subject found to be pregnant from the investigational product (Section 11).

Pregnancies will not be considered adverse events (unless the investigational product is suspected of having inhibited the effect of a contraceptive drug). The investigator or subinvestigator will conduct follow-up for all pregnancy outcomes (spontaneous abortion, induced abortion, normal delivery, delivery with congenital anomaly) and notify the sponsor. Pregnancies in the partners of male subjects will be similarly handled.

Deliveries, induced abortions, and spontaneous abortions associated with a congenital anomaly and induced abortions and spontaneous abortions because of a maternal abnormality in a female subject will be treated as serious adverse events.

# 11. Completion and Discontinuation of Treatment and Observations

# 11.1 Days of Completion and Discontinuation of Individual Subjects

When a subject completes the study, promptly enter the day of completion (i.e., the day when the final tests and observations specified in the protocol are performed) in the eCRF.

When a subject is discontinued from the study, promptly enter the day of discontinuation (i.e., the day when the final tests and observations specified in the protocol are performed) and the reason for discontinuation (select the primary and other reasons from the choices in Section 11.2.1) in the eCRF.

Determine whether oxaliplatin was discontinued and, if so, promptly enter the reason for discontinuation (CIPN/adverse event/other) in the eCRF.

#### 11.2 Discontinuation Criteria for Individual Subjects

# 11.2.1 Study Discontinuation Criteria

The investigator or subinvestigator will discontinue from the study subjects satisfying any of the following discontinuation criteria:

#### [1] Adverse event

This refers to when a subject is discontinued for an adverse event. This includes cases when a subject is discontinued by request because of an adverse event and when a subject dies because of an adverse event and cannot continue in the study.

[2] Allowable range for the postoperative adjuvant chemotherapy schedule exceeded

This refers to when a subsequent course of postoperative adjuvant chemotherapy is not started within 43 days of the start of the most recent postoperative adjuvant chemotherapy (Day 1).

# [3] Extension of study period

This refers to when the 12th course of postoperative adjuvant chemotherapy has not started as of Week 34 (239 days after the day of registration).

#### [4] Lack of efficacy

This refers to discontinuations because study procedures are not effective in the targeted disease (CIPN onset). This includes cases when the targeted disease progresses because of lack of efficacy.

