# 8.1.4 Criteria for Suspension/Resumption and Criteria for Discontinuation of the Investigational Product

- Suspend use of the investigational product when the administration of oxaliplatin is suspended.
   Resume investigational product administration concurrently with the resumption of oxaliplatin administration.
- Discontinue use of the investigational product if the administration of oxaliplatin is discontinued.

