# 8.3.2.1 Criteria for Changing Postoperative Adjuvant Chemotherapy

[1] Criteria for postponing all postoperative adjuvant chemotherapy drugs

Referring to the criteria in Table 8.3-3 before administration on the day of postoperative adjuvant chemotherapy administration in course 2 and beyond, the investigator or subinvestigator will postpone the administration of all postoperative adjuvant chemotherapy drugs until the subject's condition satisfies the criteria. The administration of all drugs may be postponed if any of the criteria for suspending oxaliplatin in Table 8.3-5 are satisfied on the day scheduled for oxaliplatin administration. If no postoperative adjuvant chemotherapy for the subsequent course is begun within 43 days of the start of the most recent postoperative adjuvant chemotherapy (Day 1), the subject will be discontinued from the study and undergo the end-of-study evaluations.

Table 8.3-3 Criteria for postponing all postoperative adjuvant chemotherapy drugs

Туре	Initiation criteria
Neutrophil count	$\geq 1,500/\text{mm}^3$
Platelet count	$\geq$ 75,000/mm 

[2] Criteria for reducing the dose of oxaliplatin and fluorouracil in association with adverse events

If a subject experiences an adverse event, the investigator or subinvestigator will reduce the dose
of oxaliplatin and fluorouracil in reference to the following criteria:

Table 8.3-4 Criteria for reducing the dose of oxaliplatin and fluorouracil in association with adverse events

Туре	Greatest severity	Next dose
Neutrophil count	<500/mm 	Reduce oxaliplatin dose to 75 mg/m 
Platelet count	<50,000/mm 	Reduce fluorouracil dose by 20%
Gastrointestinal tract adverse	≥Grade 3 a)	
events (occurring despite		
prophylactic treatment)		

a) NCI-CTCAE

- [3] Criteria for suspending or reducing the dose of oxaliplatin in association with peripheral neuropathy

  The investigator or subinvestigator will determine the dose of oxaliplatin according to the criteria
  in Table 8.3-5 on Day 1 of each course.
  - If reducing the oxaliplatin dose, do not increase the dose even if the CTCAE grade improves.
  - After suspending oxaliplatin, resume treatment at the dose of 75 mg/m².
     The investigator or subinvestigator need not comply with these criteria when determining that other criteria are necessary to ensure subject safety.

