Table 8.3-5 Criteria for suspending or reducing the dose of oxaliplatin in association with peripheral neuropathy

Greatest NCI-CTCAE*1 grade after previous oxaliplatin dose	Day 1 NCI-CTCAE grade (day of evaluation)	Action to take for oxaliplatin
≤Grade 1	≤Grade 1	Do not reduce dose or suspend.
≥Grade 2	≤Grade 1	Do not reduce dose or suspend.  (The dose may be reduced to 75 mg/m  .)
Any	Grade 2	Reduce the dose to 75 mg/m  .  (Treatment may be suspended.)
Any	≥Grade 3	Treatment may be suspended.

\*1 Assess the NCI-CTCAE grade of the more severe of peripheral motor neuropathy or peripheral sensory neuropathy.

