#### 11.3 Rationale for Discontinuation Criteria

These criteria were established to respect the wishes of the subjects, ensure safety, avoid influencing evaluations, and honor subject circumstances.

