# 11.4.2 Procedures for Post-registration Discontinuations

After deciding to discontinue a subject who has been registered from the study, the investigator or subinvestigator will:

- [1] Promptly inform the affected subject and, if the subject is receiving the investigational product, promptly discontinue treatment on determining that any of the above discontinuation criteria in Section 11.2.1 are applicable.
- [2] Promptly administer the appropriate treatment to the affected subject when a subject is discontinued for an adverse event, worsening of symptoms, or other incident.
- [3] Promptly perform the observations and tests/evaluations scheduled for treatment-period discontinuations if the subject is discontinued during the treatment period. Assess the reason for discontinuation as in Section 11.2.
  - If the evaluation at treatment period discontinuation takes place on or after Day 43 of the last course of postoperative adjuvant chemotherapy, or if the subsequent tests/observations for the

- study are not possible, perform the study completion evaluations instead of the treatment-period discontinuation evaluations.
- If the evaluation at treatment-period discontinuation takes place on or before Day 42 of the last course of postoperative adjuvant chemotherapy, have the subject re-visit on Day 43 of the last course of postoperative adjuvant chemotherapy and perform the end-of-study evaluations.
- [4] Promptly perform the observations and tests/evaluations scheduled for end of study if the subject is discontinued during the follow-up period. Assess the reason for discontinuation as in Section 11.2.
- [5] If a subject is discontinued for not visiting, inquire about the reason and condition after last visit by telephone, written correspondence, or another means whenever possible.
- [6] Promptly notify the sponsor of the study discontinuation.

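### Criterion [4] in Section 11.2.1 lets CIPN itself end study participation, with no threshold, so later-course summaries can lose subjects with more neuropathy (low severity, optional improvement)

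*Protocol*

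**What the plan says.** Protocol Section 11.2.1 opens with "The investigator or subinvestigator will discontinue from the study subjects satisfying any of the following discontinuation criteria" and lists eleven items. Item [4], lack of efficacy, reads "This refers to discontinuations because study procedures are not effective in the targeted disease (CIPN onset"), and its second sentence adds progression of the disease. It gives no grade, duration or scale. Section 11.1 has staff record the reason for leaving in the eCRF ("select the primary and other reasons from the choices in Section 11.2.1"). The procedure in Section 11.4.2 begins "After deciding to discontinue a subject who has been registered from the study". Section 11.3 gives one rationale for the whole list: "These criteria were established to respect the wishes of the subjects, ensure safety, avoid influencing evaluations, and honor subject circumstances".

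For an exit during treatment, Section 11.4.2 [3] provides a discontinuation evaluation and, if that falls on or before Day 42, one further visit on Day 43 of the last course.

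Elsewhere CIPN is handled without leaving the study:
- Section 8.3.2.1 [3] and Table 8.3-5 set the "Criteria for suspending or reducing the dose of oxaliplatin in association with peripheral neuropathy". Even at Grade 3 or greater, suspension is optional, and treatment resumes at 75 mg/m².
- Section 8.1.4 says "Discontinue use of the investigational product if the administration of oxaliplatin is discontinued", with no study exit attached.
- Section 8.4.2 lifts drug restrictions at Grade 2 or greater, and Section 9.2.5 adds unscheduled CIPN evaluations.
- Table 8.3-2 foresees stopping only some of the mFOLFOX6 drugs. The 43-day rule in Section 8.3.2.1 [1] ends participation only in this case: "If no postoperative adjuvant chemotherapy for the subsequent course is begun within 43 days".

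Section 12.6.1 makes descriptive statistics at each time point the main efficacy analysis. Section 12.4 leaves missing continuous data unimputed, with LOCF as a sensitivity analysis.

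**The concern.** CIPN is both the efficacy outcome and, under [4], a permitted reason to stop measuring it. No threshold is set, so each investigator decides how much neuropathy justifies an exit. Section 3.3.1 [8] says that twelve courses were chosen so that chronic neuropathy could be evaluated, and Section 1.1.3 says that its risk rises with cumulative oxaliplatin dose. The later courses therefore matter most for that aim. If the more affected subjects leave before then, the late time points describe a milder group than the one randomized. LOCF keeps the last value before exit and cannot show later worsening.

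Exit is not needed to protect the subject from further drug, because product and oxaliplatin can both be stopped on study.

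**Working it through.** **1. The plan's own figure.** Section 12.1 gives 25 per group for ±20% precision. With a proportion of 0.5 (assumed; not stated) and 95% confidence, n = 1.96² × 0.5 × 0.5 / 0.20² = 24.01, rounded up to 25. At n = 25 the half-width is 19.6 points. The figure reproduces.

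**2. Assessments kept.** Inputs are the time points in Sections 9.6.3.1 to 9.6.3.3 and 9.6.3.5, with no postponements. The last course before exit is n, and the discontinuation and Day 43 visits are counted.
- FACT/GOG-NTX-12 and NRS: two per course, so 2n + 2 on exit; 26 in full.
- DEB-NTC: one per course, so n + 2; 14 in full.
- NCI-CTCAE: three per course, so 3n + 2; 38 in full.
- NCI-CTCAE if oxaliplatin stops after course n but other drugs continue to course 12, with Days 2 and 3 waived: 3n + (12 − n) + 2.

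| Last course n | FACT/GOG-NTX-12, NRS: exit / stay | DEB-NTC: exit / stay | NCI-CTCAE: exit / stay |
|---|---|---|---|
| 4 | 10 / 26 | 6 / 14 | 14 / 22 |
| 6 | 14 / 26 | 8 / 14 | 20 / 26 |
| 8 | 18 / 26 | 10 / 14 | 26 / 30 |
| 10 | 22 / 26 | 12 / 14 | 32 / 34 |

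The NCI-CTCAE "stay" column assumes that footnote a of Table 9.1-1, which speaks of suspended oxaliplatin, also covers discontinued oxaliplatin. If it does not, that column is 38 throughout.

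**3. Bias in one arm's late-course proportion.** All inputs are assumed. Let p be the true proportion with Grade 2 or greater and q the share of those cases who leave. The proportion among those remaining is p(1 − q)/(1 − pq), and the number remaining is 25(1 − pq).

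| p | q = 0.10 | q = 0.25 | q = 0.50 |
|---|---|---|---|
| 0.30 | 27.8% (−2.2) | 24.3% (−5.7) | 17.6% (−12.4) |
| 0.50 | 47.4% (−2.6) | 42.9% (−7.1) | 33.3% (−16.7) |
| 0.60 | 57.4% (−2.6) | 52.9% (−7.1) | 42.9% (−17.1) |

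The 95% half-widths of these proportions run from 16 to 23 points. If half of these exits would happen anyway under [6] or [10], replacing q by q/2 shows that the fix recovers 1 to 10 points. For example, at p = 0.60 and q = 0.50 it recovers 52.9 − 42.9 = 10 points.

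**4. Effect on the difference between arms, same q in both.**
- 50% v 30%: the true 20 points becomes 19.5, 18.5 or 15.7, a loss of 0.5, 1.5 or 4.3.
- 40% v 25%: loss of 0.6, 1.7 or 4.3.
- 30% v 20%: loss of 0.5, 1.5 or 3.5.
- 60% v 40%: loss of 0.1, 0.4 or 2.1.

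For 50% v 30% with 25 per arm, the 95% half-width of the difference is 1.96 × √(0.25/25 + 0.21/25), about 27 points.

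**5. Continuous scales.** If a fraction f of an arm leaves and the leavers are d SD worse than those who stay, the mean shifts by f × d. With f = pq = 0.05 to 0.25 (p = 0.50) and d = 0.5 to 1, the shift is 0.025 to 0.25 SD, against a standard error of 1/√25 = 0.20 SD. With 30% on active, the two fractions differ by 0.02 to 0.10, so the difference between arms moves by 0.01 to 0.10 SD, against a standard error of √2 × 0.20 = 0.28 SD. A simulation agrees in order of magnitude. It assumed mean declines of 1.0 and 0.5 SD, with 10% to 50% of subjects declining by more than 1 SD leaving. The difference fell from 0.50 to between 0.49 and 0.44 SD.

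**The case against.** The strongest reply is that [4] is a reason label, not a rule that removes people. The list also contains items that only classify exits, such as loss to follow-up and subject request. Item [4] describes discontinuations, Section 11.1 uses the list as eCRF choices, and Section 11.4.2 starts once a decision has been made. This stands. A reader might infer from the lead-in to Section 11.2.1 that every subject with CIPN must be withdrawn. With acute neuropathy expected in 85% to 95% (Section 1.1.3), that would nearly empty the study and make Table 8.3-5 and Sections 8.4.2 and 9.2.5 pointless. The document as a whole does not support it. The discretionary reading still permits withdrawal because of the outcome.

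Second, safeguards exist. The two remaining visits collect every efficacy scale. Missing Grade 1 or greater status counts as an event. Kaplan-Meier curves are planned for Grade 1 and Grade 2 or greater, and dropout analyses may be done as necessary (Section 12.6.2.7). These largely protect the incidence results. They do not replace later-course scale values that were never collected.

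Third, CIPN is not an adverse event here (Section 9.7.4.1), so [4] is the only CIPN-specific exit code. Deleting it would hide efficacy-related dropout. This is right, and it shapes the fix. So is the related point that a CIPN-based product-stopping rule in Section 8.1.4 would let product stop because of the outcome while oxaliplatin continues.

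Finally, the conflict with Section 11.3 is weak, since that sentence gives several aims for the whole list.

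**Conclusion.** The point holds in a limited form. Section 11.2.1 [4] permits an exit because of CIPN, without a threshold. Such an exit ends course-by-course assessment and sits badly with on-study CIPN management and the reason for choosing twelve courses. The harm is confined mainly to later-course summaries by time point. Ever-incidence of Grade 1 or greater, and of Grade 2 or greater already reached before exit, is little affected.

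The size is unknown and probably modest. The visit counts follow from the schedule, but every bias figure rests on assumed exit rates, and the 17-point extreme needs half of all Grade 2 or greater cases to leave. A reader might infer that the treatment comparison is materially biased. The working does not show that: with equal exit shares in both arms, the effect is small beside the sampling error. Unequal shares could change its direction, and the protocol gives nothing to settle that. In an exploratory, mainly descriptive study this is a low-severity, optional improvement.

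**What to change.** Change the wording of Section 11.2.1 as follows:
- State that CIPN onset or progression alone is not a ground for ending study participation.
- State that subjects whose oxaliplatin is stopped for CIPN, and whose product therefore stops under Section 8.1.4, stay on the existing assessment schedule while any adjuvant chemotherapy continues.
- Keep CIPN or lack of efficacy only as a recorded reason when a subject leaves under [6] or [10], so that efficacy-related dropout stays identifiable.

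Leave [2], [3], [6] and [10] as exit routes, and add no CIPN-based product-stopping rule to Section 8.1.4. It would help to say whether footnote a of Table 9.1-1 also covers courses after oxaliplatin is discontinued.

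No new visit or assessment type is needed. The cost is somewhat longer participation for the few subjects who would have left under [4]. Some will still leave by request or for safety, so the gain is partial.

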# [5] Subject lost to follow-up

This refers to when subsequent tests and observations (including follow-up by telephone) are not possible because the subject is unable to visit.

# [6] Discontinued by investigator or subinvestigator

This refers to when the physician finds a subject unsuited to study continuation for a reason in another category.

#### [7] Major protocol deviation

This refers to when the subject is discontinued on the identification of a major protocol deviation (GCP violation, inclusion/exclusion criteria violation, drug number violation, multiple registrations).

# [8] Subject ineligible at screening

This refers to discontinuations, taking place before assignment, according to the inclusion/exclusion criteria.

# [9] Identification of pregnancy

This refers to when the subject is found to be pregnant during the treatment period.

# [10] By subject request

This refers to when a subject is discontinued by request.

#### [11] Per decision by sponsor

This refers to when a subject is discontinued after the sponsor submits a notification such as to completely or partially terminate or suspend the study or terminate the study at a study site. Termination of the study at a study site includes cases in which an investigator transfer or study site closure complicates study continuation by a subject in the opinion of the sponsor.

#### 11.3 Rationale for Discontinuation Criteria

These criteria were established to respect the wishes of the subjects, ensure safety, avoid influencing evaluations, and honor subject circumstances.

#### 11.4 Discontinuation Procedures

# 11.4.1 Procedures for Study Discontinuation from Informed Consent to Before Registration

The investigator or subinvestigator will perform discontinuations according to the following procedures if a subject must be discontinued from the study from the time of informed consent to before registration.

- [1] Promptly inform the affected subject of discontinuation and state in the medical records that the subject was discontinued on determining that any of the discontinuation criteria in Section 11.2.1 are applicable (criteria 1 and 6 to 11).
- [2] Promptly notify the sponsor of the discontinuation. The investigator or subinvestigator will promptly enter the information in Section 7.2.1 and the reason for discontinuation in the IWRS and then send the data to the subject registration center. All complications and adverse events up to the time of discontinuation will be recorded in the eCRF.

# 11.4.2 Procedures for Post-registration Discontinuations

After deciding to discontinue a subject who has been registered from the study, the investigator or subinvestigator will:

- [1] Promptly inform the affected subject and, if the subject is receiving the investigational product, promptly discontinue treatment on determining that any of the above discontinuation criteria in Section 11.2.1 are applicable.
- [2] Promptly administer the appropriate treatment to the affected subject when a subject is discontinued for an adverse event, worsening of symptoms, or other incident.
- [3] Promptly perform the observations and tests/evaluations scheduled for treatment-period discontinuations if the subject is discontinued during the treatment period. Assess the reason for discontinuation as in Section 11.2.
  - If the evaluation at treatment period discontinuation takes place on or after Day 43 of the last course of postoperative adjuvant chemotherapy, or if the subsequent tests/observations for the

- study are not possible, perform the study completion evaluations instead of the treatment-period discontinuation evaluations.
- If the evaluation at treatment-period discontinuation takes place on or before Day 42 of the last course of postoperative adjuvant chemotherapy, have the subject re-visit on Day 43 of the last course of postoperative adjuvant chemotherapy and perform the end-of-study evaluations.
- [4] Promptly perform the observations and tests/evaluations scheduled for end of study if the subject is discontinued during the follow-up period. Assess the reason for discontinuation as in Section 11.2.
- [5] If a subject is discontinued for not visiting, inquire about the reason and condition after last visit by telephone, written correspondence, or another means whenever possible.
- [6] Promptly notify the sponsor of the study discontinuation.

